8.4.1 Visit 26 (Week 25 or Week 77 or PEOT)

The following procedures will be performed at Visit 26 (Week 25 or Week 77 or PEOT):

- PROs should be conducted in the order specified in Section 10.4:
 - iRODS assessment – to be performed before any other assessment
 - Fatigue scale
 - CIDP PRO instrument
 - PGIS
 - PGIC
- Query for suicidality
- Withdrawal criteria assessment
- Prior and concomitant medications
- Concomitant medical procedures
- Vital signs (taken once during the visit)
- Body weight
- 12-lead ECG
- Recording of AEs
- Brief physical examination
- Brief neurological examination
- Urine sample for urinalysis
- Urine pregnancy test for women of childbearing potential
- Blood sample (all samples should be taken predose unless otherwise specified; the laboratory manual will provide guidance on the order of sample collection) for:
 - Clinical laboratory tests (ie, hematology and clinical chemistry)
 - PK of rozanolixizumab
 - ADA (anti-rozanolixizumab antibodies)

- Immunoglobulins (total IgG, IgG subclasses)
- NF-L (Visit 26 [Week 25] only or PEOT only if Treatment Period 1 is performed)
- IgA, IgM, IgE
- CIDP specific auto-antibodies (Visit 26 [Week 25] only or PEOT only if Treatment Period 1 is performed)
- Vaccination-specific antibody titers (tetanus and influenza Type A)
- Contact IRT
- INCAT assessment
- RT-MRC assessment (Visit 26 [Week 25] only)
- Assessment of grip strength by site personnel

8.4.2 Visits 27 and 28 (Weeks 27 and 29, and at 79 and 81), Home Visits

The following procedures will be performed at Visits 27 and 28 (Weeks 27 and 29, and at 79 and 81) by a healthcare professional visiting the study participant at his/her home:

- Query for suicidality
- Withdrawal criteria assessment
- Prior and concomitant medications
- Concomitant medical procedures
- Vital signs (taken once during the visit)
- Recording of AEs
- Urine pregnancy test

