^s Trough PK samples should be taken for all study participants receiving rozanolixizumab. At Visits 2, 4, and 8, PK samples should be taken predose and 4h postdose for all study participants. At Visits 14, 18, 22 and quarterly at site visits during Treatment Period Part 2, a predose sample only should be taken. At Visit 26, samples to be taken once during the visit.

^t Does not apply to Visit 10.

^u Serum complement (C3, C4), plasma complement (C3a, C5a), and serum cytokines should be taken predose at Visit 2 for all study participants. Samples should be taken predose and 4h postdose for all study participants at other scheduled visits (Visits 3, 8, 10, 14, 18, 22 and at first (Week 25) and last visit (Week 73) of Treatment Period Part 2); if an infusion reaction occurs within the first 2h, refer to Section 5.2.1 and Table 5-2.

^v Only at Visit 14.

^w In case IgG levels are below 2 and the study participant does not qualify for a withdrawal, IgG levels will be monitored weekly.

^x Assessments to be performed only at the first visit after Visit 25 (ie, 1st visit of Part 2). Visit 29/FV should not be performed after Treatment Period 2.

^y Only performed at PEOT visit when starting Observation Period directly after Treatment Period Part 1

^z At Visits 2, 3, 8, 10, 14, 18, and 22, samples for exploratory biomarkers should be taken predose. See [Table 5-2](#) for sampling in case of AE of interest.

This document cannot be used to support any marketing authorization application and any extensions or variations thereof
PUBLIC COPY

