8.2.9 Visits 10, 14, 18, and 22 (Weeks 9, 13, 17, and 21)

The following procedures will be performed at Visits 10, 14, 18, and 22 (Weeks 9, 13, 17, and 21):

- PROs should be conducted in the order specified in Section 10.4:
 - iRODS assessment – to be performed before any other assessment

- CIDP PRO instrument
- Fatigue scale
- PGIS
- PGIC
- Query for suicidality
- Withdrawal criteria assessment
- Prior and concomitant medications
- Concomitant medical procedures
- Vital signs (prior to IMP administration, at the end of the infusion, at 2h after the end of the infusion)
- 12-lead ECG
- Recording of AEs
- Brief physical examination
- Brief neurological examination
- Urine sample for urinalysis and urine pregnancy test
- Blood sample (all samples should be taken predose unless otherwise specified; the laboratory manual will provide guidance on the order of sample collection) for:
 - Clinical laboratory tests (ie, hematology and clinical chemistry)
 - PK of rozanolixizumab (does not apply to Visit 10)
 - ADA (anti-rozanolixizumab antibodies) (does not apply to Visit 10)
 - Serum complement (C3, C4) and plasma complement (C3a, C5a) (predose and 4h postdose)
 - Serum cytokines (predose and 4h postdose)
 - Vaccination-specific antibody titers (tetanus and influenza Type A) (only at Visit 14)
 - Immunoglobulins (total IgG and IgG subclasses)
 - IgA, IgM, IgE
 - CIDP-specific auto-antibodies
 - Exploratory biomarker analysis
- Contact IRT
- Administer IMP
- INCAT assessment
- RT-MRC assessment

- Assessment of grip strength by site personnel

8.2.10 Home Visits 11 to 13, 15 to 17, 19 to 21, and 23 to 25 (Weeks 10 to 12, 14 to 16, 18 to 20, and 22 to 24)

The following procedures will be performed at Visits 11 to 13, 15 to 17, 19 to 21, and 23 to 25 (Weeks 10 to 12, 14 to 16, 18 to 20, and 22 to 24) by a healthcare professional visiting the study participant at his/her home:

- Query for suicidality
- Tuberculosis Signs and Symptoms Questionnaire (only at Visit 13, 17, 21, and 25)
- Withdrawal criteria assessment
- Prior and concomitant medications
- Concomitant medical procedures
- Vital signs (prior to IMP administration, at the end of the infusion, at 2h after the end of the infusion)
- Recording of AEs
- 12-lead ECG (only at Visits 12, 16, 20, and 24)
- Blood sample for clinical laboratory tests (ie, hematology and clinical chemistry) (only at Visits 12, 16, 20, and 24)
- Urine sample for urinalysis (only at Visits 12, 16, 20, and 24)
- Urine pregnancy test

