8.3 Treatment Period Part 2 (Weeks 25 to 76)

Entry into the Treatment Period (Part 2) will be subject to a careful individual assessment of the benefit-risk for each study participant completing Treatment Period (Part 1) following a discussion with the Sponsor's Medical Monitor and/or Study Physician. The first visit of Treatment Period Part 2 will be performed at site at Week 25 followed by 3 weekly visits at the study participant's home. This sequence will be repeated until the end of the Treatment Period Part 2. The visits during this period will be numbered sequentially.

Study participants may choose to self-administer the IMP during Treatment Period 2 under supervision of a nurse and after having received appropriate training.

8.3.1 Additional site visits during maximum 52-week Treatment Period Part 2 (monthly starting at Week 25) or until availability of an Access Program (whichever comes first)

The first visit of Treatment Period Part 2 will be performed on site at Week 25. Site visits will be performed monthly. The following procedures will be performed at monthly frequency unless otherwise defined:

- PROs should be conducted in the order specified in Section 10.4:
 - iRODS assessment – to be performed before any other assessment
 - Fatigue scale (every 24 weeks)
 - CIDP PRO instrument (every 24 weeks)
 - PGIS (every 24 weeks)
 - PGIC (every 24 weeks)
- Query for suicidality
- Tuberculosis Signs and Symptoms Questionnaire (every 12 weeks)
- Withdrawal criteria assessment
- Prior and concomitant medications
- Concomitant medical procedures
- Vital signs (prior to IMP administration, at the end of the infusion)
- Body weight (Week 25 and Week 49)
- Recording of AEs
- Brief physical examination
- Brief neurological examination
- 12-lead ECG (on-site visits only [Weeks 25, 37, 49, 61])
- Blood sample (all samples should be taken predose unless otherwise specified; the laboratory manual will provide guidance on the order of sample collection) for:
 - Clinical laboratory tests (ie, hematology and clinical chemistry)
 - PK of rozanolixizumab (on-site visits only [Weeks 25, 37, 49, 61])
 - ADA (anti-rozanolixizumab antibodies) (on-site visits only [Week 25, 37, 49, 61])
 - Serum complement (C3, C4) and plasma complement (C3a, C5a) (predose and 4h postdose) (at Weeks 25 and 73)
 - Serum cytokines (predose and 4h postdose) (at Weeks 25 and 73)

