 - Vaccination-specific antibody titers (tetanus and influenza Type A) (on-site visits only [Weeks 25, 37, 49, 61])
 - Immunoglobulins (total IgG and IgG subclasses)

- IgA, IgM, IgE (on-site visits only [Weeks 25, 37, 49, 61])
- NF-L (only at Week 25)
- CIDP specific auto-antibodies (only at Week 25)
- Urine pregnancy test
- Contact IRT
- Administer IMP – self-administration by the study participant under the supervision of the nurse (to confirm that study participant is proceeding correctly) may be considered provided the participant is willing to do so, the participant has been adequately trained by the site personnel according to Self-administration training guidance document
- INCAT assessment
- Assessment of grip strength by site personnel

8.3.2 Additional home visits during Treatment Period Part 2 (weekly in between site visits starting at Week 26 or until availability of an Access Program (whichever comes first)

The following procedures will be performed during the Treatment Period Part 2 by a healthcare professional visiting the study participant at his or her home. Visits will be performed weekly in between monthly site visits (Section 8.3.1):

- Withdrawal criteria assessment
- Prior and concomitant medications
- Concomitant medical procedures
- Vital signs (prior to IMP administration, at the end of the infusion)
- Recording of AEs
- Contact IRT
- Administer IMP (unless IMP is temporarily discontinued (see Section 6.4.1.3) – self-administration by the study participant under the supervision of the home nurse may be considered provided the participant is willing to do it and has been adequately trained by the site personnel according to Self-administration training guidance document.

8.4 Observation Period, Visits 26 to 29 (Weeks 25 to 32 study participants completing Treatment Period Part 1 only and Weeks 77 to 84 for study participants completing Treatment Period Part 1 and Part 2)

Following the final dose of rozanolixizumab at Week 24 (Visit 25) or Week 76, 4 subsequent visits will be scheduled over 8 weeks (Visits 26 to 29) to collect safety and efficacy data for study-related outcome measures and procedures unless the study participant continues rozanolixizumab treatment under an Access Program or equivalent. In the latter case, only the PEOT Visit (Visit 26) will be performed. Visit 27 and Visit 28 are home nursing visits to be

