8.5 Premature end of treatment and Final Visit

All study participants who withdraw early from the Treatment Period should attend a PEOT Visit, which will be scheduled as close as possible to the date of the decision for the study or treatment withdrawal.

Study participants are encouraged to complete all visits of the Observation Period following the PEOT Visit by either coming to the clinic or as home nursing visits, if appropriate.

In case a study participant is not willing to attend the visits in the Observation Period, the study participant should still be strongly encouraged to attend at least the PEOT Visit and the FV.

The FV should be scheduled 8 weeks after their final dose of IMP.

The assessments to be done at the PEOT Visit and the FV are the same as those at Visit 26 and Visit 29, respectively.

A study participant entering the Access Program after completion of part or full Treatment Period 2 without any relapse will not complete the Observation Period but will only perform the PEOT/V26 one week after the last IMP dispensing for the study.

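### Protocol Section 8 contradicts Table 5-1 on RT-MRC at Week 25 for participants entering Part 2 and at PEOT for early stops in Part 1

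*Protocol*

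**What the plan says.** **Table 5-1 (Protocol 5.2).** The RT-MRC row has an entry with footnote x in the Part 2 site-visit column and one with footnote y in the Visit 26/PEOT column. Footnote x reads "Assessments to be performed only at the first visit after Visit 25 (ie, 1st visit of Part 2", which is Week 25. Footnote y reads "Only performed at PEOT visit when starting Observation Period directly after Treatment Period Part 1". NF-L and CIDP-specific auto-antibodies carry the same footnotes in the same columns.

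**Section 8.3.1 (Part 2 site visits).** The list opens with "The following procedures will be performed at monthly frequency unless otherwise defined". It includes iRODS, INCAT and grip strength, and it gives the other two footnote-x items as Week 25 items, for example "CIDP specific auto-antibodies (only at Week 25". It has no RT-MRC line.

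**Section 8.4.1 (Visit 26: Week 25, Week 77 or PEOT).** The RT-MRC line is "RT-MRC assessment (Visit 26 [Week 25] only". The NF-L line goes further: "NF-L (Visit 26 [Week 25] only or PEOT only if Treatment Period 1 is performed". The auto-antibody line has the same PEOT clause.

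**Section 8.5.** "The assessments to be done at the PEOT Visit and the FV are the same as those at Visit 26 and Visit 29, respectively". This sends PEOT back to the 8.4.1 list, with its Week 25 limit on RT-MRC.

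**Use of the data.** Protocol 4.2.1 makes the RT-MRC sum score and its change from Baseline an efficacy variable at every scheduled assessment. SAP 8.6 summarises it by visit. SAP 4.2.1 maps PEOT efficacy data to the closest missing visit, up to Visit 26.

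**The concern.** The protocol gives sites two instructions for the same assessment. A site that prepares its visit checklists from Section 8 would skip RT-MRC at Week 25 for everyone entering Part 2, and at PEOT for anyone stopping early in Part 1.

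What goes missing would not be random. Entry to Part 2 depends on a favourable individual benefit-risk assessment (Protocol 5.1 and 8.3), so the Week 25 values left would come from a selected group. Early stoppers include participants who relapse or are rescued, because Protocol 6.4 requires them to discontinue IMP. For them the SAP's PEOT mapping would have no RT-MRC value to place. If sites differ in which text they follow, missingness would also vary by site. A muscle-strength examination that was not done at a visit cannot be recovered later.

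**Working it through.** The plan states no figure on this point, so the check compares the texts and then bounds the loss.

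**1. Items sharing footnotes x and y**

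| Item | Table 5-1, Part 2 site visit | Table 5-1, Visit 26/PEOT | Section 8.3.1 | Section 8.4.1 |
|---|---|---|---|---|
| NF-L | x | y | Week 25 | Week 25, plus PEOT clause |
| Auto-antibodies | x | y | Week 25 | Week 25, plus PEOT clause |
| RT-MRC | x | y | absent | Week 25, no PEOT clause |

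No reason is given for treating RT-MRC differently. It looks like a drafting omission.

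**2. Who has RT-MRC at the end of Part 1 or at an early stop**

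| Participant | Under Table 5-1 | Under Section 8 |
|---|---|---|
| Completes Part 1, does not enter Part 2 | Yes, Visit 26 (Week 25) | Yes |
| Enters Part 2 | Yes, first Part 2 visit (Week 25) | No |
| Stops early in Part 1, then Observation Period | Yes, PEOT | No |

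The sources agree for the first group and conflict for the other two.

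**3. Resulting gaps under Section 8.** The last Part 1 list with RT-MRC covers Visit 22 (Week 21): "The following procedures will be performed at Visits 10, 14, 18, and 22 (Weeks 9, 13, 17, and 21".
- Participants completing all of Part 2: the next listed value is the Final Visit in 8.4.3, so 84 − 21 = 63 weeks. Under Table 5-1 the next value after Week 21 is Week 25, so 25 − 21 = 4 weeks.
- Access Program entrants have no Final Visit (5.1, 8.5), so they have nothing listed after Week 21.
- Early Part 1 stoppers: from Week 9 the site visits are 13 − 9 = 4 weeks apart, so the last RT-MRC can be up to about 4 weeks old at the stop. The next listed value is the Final Visit, 8 weeks after the last dose.

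The 63-week figure relies on 8.4.3 listing RT-MRC at Week 84. Footnote x, which also marks RT-MRC at the Final Visit, says that visit should not be performed after Part 2. That is a related mismatch.

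**4. Size of the Week 25 loss.** Let c be the share of Part 1 completers who enter Part 2, and s the share of those continuers at sites following Section 8. Assume that everyone attends Week 25.
- Share of Week 25 values lost = c × s.
- Share of the recorded values that come from non-continuers = (1 − c) / (1 − c × s).

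The documents give neither c nor s. Taking c = 0.6 to 0.9 purely as an assumption:
- s = 0: loss 0; non-continuers supply 1 − c = 0.40 down to 0.10 of the values.
- s = 1: loss 0.60 to 0.90; non-continuers supply (1 − c) / (1 − c) = all of the values.

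**The case against.** The strongest reply is that Table 5-1 governs. Section 5.1 says that the table holds the assessments for each visit, Section 8 describes itself as an outline, and Section 10.5 ties RT-MRC timing to the table. This stands as far as it goes: the protocol as a whole does schedule these assessments, and the defect is a contradiction, not an absence. It does not remove the problem. Section 8 says that its listed procedures will be performed, and an explicit *only* reads as an instruction. Section 6.4 sends participants who stop to both Table 5-1 and 8.4.1, as if the two agreed.

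Three stronger readings are tempting, and the documents do not support them.

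- *Relapsers leave with no strength measurement.* The 8.4.1 list requires grip strength, INCAT and iRODS at PEOT without restriction. Only RT-MRC is affected, and it is not one of the relapse criteria.
- *Deterioration goes unmeasured just when it occurs.* Every Part 1 site-visit list that has the three relapse measures also has RT-MRC, so a relapse found at a scheduled Part 1 site visit has a same-day value. For a stop at Week 10, RT-MRC was due at Week 9. The gap concerns stops between those visits.
- *Early stoppers never have another RT-MRC.* Section 8.4.3 lists it at the Final Visit, which they are strongly encouraged to attend. That value is off treatment, however, and participants may be back on standard of care. Under SAP 3.9 and 4.2.1, an efficacy value after first rescue intake is listed but not summarised. The same rule would exclude a PEOT value taken after rescue.

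**Conclusion.** Sections 8.3.1 and 8.4.1 conflict with Table 5-1 footnotes x and y in the current protocol text, and 8.5 does not resolve it. Where sites follow Section 8, Week 25 RT-MRC comes only from Part 1 completers who do not continue, and early Part 1 stoppers have no RT-MRC at PEOT for the SAP mapping.

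A reader might infer that most Week 25 values will be lost. The documents do not support a figure: the loss is c × s, and it is zero if every site follows the table. The selection problem does not depend on the assumed value of c, but it does require some sites to follow Section 8.

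The consequence is limited. The primary variable is the occurrence of TEAEs; RT-MRC is one of several descriptively summarised efficacy variables. It is still worth correcting, because the missing values would be selective and cannot be recovered.

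**What to change.** Make two changes, by amendment or by a memo to sites:

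1. In 8.3.1, add the line *RT-MRC assessment (only at Week 25)*, matching footnote x.
2. In 8.4.1, change the RT-MRC condition to *Visit 26 [Week 25], or PEOT when the Observation Period starts directly after Treatment Period Part 1*, matching footnote y. The NF-L wording should not be copied, because its condition about Part 1 being performed is ambiguous: every treated participant enters Part 1.

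At the same time, reconcile 8.4.3 with footnote x on RT-MRC at the Final Visit after Part 2.

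The cost of the two changes is two lines of text. Both assessments are already in Table 5-1, so no procedure or visit is added and the SAP needs no change.

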8.4.3 Visit 29/FV (Week 32/84)

The following procedures will be performed at Visit 29/FV (Week 32/84):

- PROs should be conducted in the order specified in Section 10.4:
 - iRODS assessment – to be performed before any other assessment
 - Fatigue scale
 - CIDP (PRO instrument)
 - PGIS
 - PGIC
- Query for suicidality
- Prior and concomitant medications
- Concomitant medical procedures

- Vital signs (taken once during the visit)
- Body weight
- 12-lead ECG
- Recording of AEs
- Full physical examination
- Full neurological examination
- Urine sample for urinalysis
- Urine pregnancy test for women of childbearing potential
- Blood sample for (all samples should be taken predose unless otherwise specified; the laboratory manual will provide guidance on the order of sample collection):
 - Clinical laboratory tests (ie, hematology, clinical chemistry, and IGRA for active and latent TB)
 - ADA (anti-rozanolixizumab antibodies)
 - Immunoglobulins (total IgG and IgG subclasses)
 - IgA, IgM, IgE
 - CIDP-specific auto-antibodies
- Tuberculosis Signs and Symptoms Questionnaire
- Contact IRT
- INCAT assessment
- RT-MRC assessment
- Assessment of grip strength by site personnel

8.5 Premature end of treatment and Final Visit

All study participants who withdraw early from the Treatment Period should attend a PEOT Visit, which will be scheduled as close as possible to the date of the decision for the study or treatment withdrawal.

Study participants are encouraged to complete all visits of the Observation Period following the PEOT Visit by either coming to the clinic or as home nursing visits, if appropriate.

In case a study participant is not willing to attend the visits in the Observation Period, the study participant should still be strongly encouraged to attend at least the PEOT Visit and the FV.

The FV should be scheduled 8 weeks after their final dose of IMP.

The assessments to be done at the PEOT Visit and the FV are the same as those at Visit 26 and Visit 29, respectively.

A study participant entering the Access Program after completion of part or full Treatment Period 2 without any relapse will not complete the Observation Period but will only perform the PEOT/V26 one week after the last IMP dispensing for the study.

8.6 Unscheduled Visit/Telephone call

At any time, a study participant may have an unscheduled study visit/telephone call if the investigator and/or the study participant deem it necessary. An unscheduled visit may be conducted due to safety or efficacy reasons and appropriate assessments will be conducted in relation to the reason for the visit. All information, including reason for visit, any information on AEs, etc, should be collected in the source documents and recorded in the appropriate section of the eCRF.

9 ASSESSMENT OF SAFETY

9.1 Adverse events

9.1.1 Definitions

9.1.1.1 Adverse event

An AE is any untoward medical occurrence in a patient or clinical investigation study participant administered a pharmaceutical product that does not necessarily have a causal relationship with this treatment. An AE can therefore be any unfavorable and unintended sign (including an abnormal laboratory finding), symptom, or disease temporally associated with the use of a medicinal (investigational) product, whether or not related to the medicinal (investigational) product.

In order to ensure complete safety data collection, all AEs occurring during the study (ie, after the signing of the ICF), including any pretreatment and posttreatment periods required by the protocol, must be reported in the eCRF even if no IMP was taken but specific study procedures were conducted. This includes all AEs not present prior to the initial visit and all AEs that recurred or worsened after the initial visit.

Signs or symptoms of the condition/disease for which the IMP is being studied should be recorded as AEs only if their nature changes considerably or their frequency or intensity increases in a clinically significant manner as compared to the clinical profile known to the investigator from the study participant's history or the Baseline Period.

